**PRIMARY RESEARCH QUESTION:**

**Is there a difference in regional redistribution of ventilation when comparing eupneic tidal ventilation during Incentive Spirometry (I.S.) or EzPAP® lung expansion therapy in healthy adult human subjects?**

**Null hypothesis:** There is no difference in regional redistribution of ventilation when comparing eupneic tidal ventilation during Incentive Spirometry (I.S.) or EzPAP® lung expansion therapy in healthy adult human subjects?

**Alternative hypothesis:** There is a difference in regional redistribution of ventilation when comparing eupneic tidal ventilation during Incentive Spirometry (I.S.) or EzPAP® lung expansion therapy in healthy adult human subjects?

**SECONDARY RESEARCH QUESTIONS:**

**1. Is there a difference in regional redistribution of ventilation measured immediately after lung expansion therapy when compared to regional distribution of ventilation measured 5-minutes after lung expansion therapy?**

**Null hypothesis:** There is no difference in regional redistribution of ventilation measured immediately after lung expansion therapy when compared to regional distribution of ventilation measured 5-minutes after lung expansion therapy?

**Alternative hypothesis:** There is no difference in regional redistribution of ventilation measured immediately after lung expansion therapy when compared to regional distribution of ventilation measured 5-minutes after lung expansion therapy?

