### Answer/Response:

Pulmonary function is compromised following upper abdominal surgery. The incidence of post-operative pulmonary complications following upper abdominal surgery ranges between 17% and 88%, and it is a common cause of morbidity and mortality. Physicians order Incentive Spirometry (I.S.) and EzPAP® lung expansion therapy following surgery to encourage improved alveolar ventilation and to reduce risks of post-operative pulmonary complications associated with inhomogeneous distribution of ventilation during deep breathing inspiratory efforts. The primary purpose of this study is to determine if there is a difference in regional distribution of ventilation when comparing resting tidal ventilation with Incentive Spirometry (I.S.) and EzPAP® lung expansion therapy in healthy adult human subjects. We are also interested in determining if regional redistribution of ventilation is time dependent. Lung volume areas of interests include ventral, mid-ventral, mid-dorsal, and dorsal regions. Our null hypotheses is that there is no difference.

A convenience sampling of study participants will be invited to participate in our descriptive observational study. Study participants will be randomly allocated to receive I.S. or EzPAP® therapy after informed consent has been obtained. Electrical Impedance Tomography (EIT) monitoring will be used to visualize and measure regional distribution of ventilation during lung expansion therapy.

EIT lung monitoring and descriptive data will be presented as number (%), mean (SD), or median (IQR) as appropriate. To test our primary hypothesis, the difference between continuous level data will be analyzed with one-way multivariate analysis of variance. This is a proof of concept study that will include 30 human subjects. Statistical significance is set at  $\leq 0.0125$ . We have created a password protected SPSS file (SPSS v.23; Chicago, IL) that will be used for this study's data entry codebook and statistical output generator.

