Evaluating the effectiveness of lung expansion therapy relies upon global parameter measures such as pulse oximetry oxygen saturation and/or arterial blood gas measurements, chest wall auscultation, and assessment of sputum expectoration following therapy sessions. These global parameters do not provide the sensitivity necessary to evaluate regional lung function responses to therapy, as can be viewed with a chest x-ray or CT image. These diagnostic images provide a static view for regional lung volume assessment. They also rely upon the use of radiation. In our study, we will use Electrical Impedance Tomography (EIT) monitoring to measure regional distribution of ventilation during I.S. and EzPAP® lung expansion therapy to better understand how air travels through ventral, mid-ventral, mid-dorsal, and dorsal lung regions and to determine if redistribution of lung volume is time dependent. This non-invasive, non-radioactive/non-radiation producing, technology will provide real time quantifiable data that may be used to explore whether there is a difference in preferential regional distribution of ventilation when comparing resting eupneic ventilation to I.S. and EzPAP lung expansion therapy. We will also evaluate whether there is a difference in regional distribution of ventilation measured immediately after the third lung expansion therapy breathing sequence and post-lung expansion therapy session baseline measurement.

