**Answer/Response:**

The focus of this study is to use electrical impedance tomography (EIT) monitoring to determine if there is a difference in regional distribution of ventilation when comparing Incentive Spirometry (I.S.) to EzPAP® lung expansion therapy.

Baseline characteristics will be reported as:

- Sex (M/F): n (%)
- Age (years): m (SD)
- Weight (BMI): m (SD) or M (IQR) depending upon normality of data distribution
- Tobacco History: n (%); Never smoked, Current smoker; Former smoker
- Respiratory Related Comorbidities: n (%)

Baseline and post-lung expansion therapy dependent variable metrics will be reported as end-expiratory lung volume impedance (EELI) for each of the following ventilation regions of interest:

- Ventral (Level of measurement- continuous)
- Mid-ventral (Level of measurement- continuous)
- Mid-dorsal (Level of measurement- continuous)
- Dorsal (Level of measurement- continuous)

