**Incentive Spirometry procedure**

A study investigator will provide instruction on Incentive Spirometry procedure performance before supervised therapy and monitoring begins.

- Five minutes of eupneic ventilation EIT monitoring will occur before I.S. therapy commences.
- Study participants will be asked to take 10 deep breaths through the incentive spirometer’s mouthpiece, followed by a 60 second pause.
- The 10-breath cycle will be repeated three times with respiratory therapist coaching.
- Five minutes of eupneic ventilation EIT monitoring will occur following the last I.S. lung expansion therapy breath cycle.
- Incentive Spirometry therapy and monitoring session will last about 15 minutes (See image).

[figure not shown]

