**Answer/Response:**

While participants will not benefit directly from this study, we anticipate that important information will be gained from our EIT monitoring of regional distribution of ventilation. Future patients may benefit from our study findings as we hope to advance clinical understandings associated with these

IRB-HSR # 19661: A descriptive observational pilot study comparing regional distribution of ventilation during lung expansion therapy in healthy human subjects

therapies with use of EIT monitoring. Our findings also have potential to reduce the use of clinically ineffective lung expansion therapy, which has potential for more appropriate utilization of health care resources, benefitting society in general.

The potential benefit for study participants will not be realized directly since our aim is to monitor regional distribution of ventilation in response to I.S. or EzPAP® lung expansion therapy. These therapies are considered to be standards of care in post-operative surgical patients. Loss of dorsal regional lung volume (i.e., atelectasis) is an example of a post-operative pulmonary complication. EzPAP® is a lung expansion therapy that is used as an alternative to I.S. lung expansion therapy for increasing dorsal regional lung volume (i.e., functional residual capacity) in an effort to prevent or reverse atelectasis. When expiratory positive airway pressures of 5, 10, and 15 cmH2O was administered to a small group of healthy human subjects, Garrard et al. (Chest, 1978) found a positive pressure of 15 cmH2O was associated with the greatest FRC increase when compared to zero pressure and baseline FRC measurements. We are unable to identify previous research describing whether regional redistribution of ventilation is sustained after completing I.S. or EzPAP lung expansion therapy.

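### The immediate-versus-5-minute contrast can show change after therapy, but rest cancels out of it, so it cannot show whether any redistribution remains

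*Combined protocol and SAP*

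**What the plan says.** Under Hypothesis to be Tested, the only secondary research question is: "Is there a difference in regional redistribution of ventilation measured immediately after lung expansion therapy when compared to regional distribution of ventilation measured 5-minutes" after therapy. The Background describes the same comparison as one between "regional distribution of ventilation measured immediately after the third lung expansion therapy breathing sequence and post-lung expansion therapy session baseline measurement", and both of those values are post-therapy.

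The purpose is stated in two places. The Brief Summary says "We are also interested in determining if regional redistribution of ventilation is time dependent". Risk/Benefit Analysis, item 1, says that no previous research was found on "whether regional redistribution of ventilation is sustained after completing I.S. or EzPAP lung expansion therapy".

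Resting data exist. In the Incentive Spirometry procedure, "Five minutes of eupneic ventilation EIT monitoring will occur before I.S. therapy commences" and "Five minutes of eupneic ventilation EIT monitoring will occur following the last I.S. lung expansion therapy breath cycle". The EzPAP group has the same two periods. Statistical Considerations, item 2, reports baseline and post-therapy end-expiratory lung impedance for four regions, without attaching a test.

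Item 4 tests I.S. against EzPAP with an independent-samples t-test or Mann-Whitney test at a two-sided 0.0125. Item 5, the secondary plan, only refers back to item 4.

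**The concern.** Redistribution, and still more its persistence, is a change from the subject's own resting pattern. A contrast between two post-therapy readings measures change between those two moments, and nothing in it is tied to rest.

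Two conclusions are at stake. If the contrast is not significant, the data fit a redistribution that holds for 5 minutes and equally fit no redistribution at all. If it is significant, something changed after therapy, but the result does not say whether the 5-minute pattern is back at rest, part of the way back, or further from rest than before. This holds even if the contrast is analysed as a correct within-subject comparison, so it is separate from the question of whether an independent-samples test suits it.

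**Working it through.** **Inputs from the documents.** 30 subjects, two parallel arms, two-sided 0.0125, four regions, no dropout expected. No power calculation is given, so there is no planned power to reproduce. The threshold equals 0.05/4 = 0.0125, which fits a family-wise 0.05 over four regions, although the documents do not state this.

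**Step 1: algebra.** Let R, I and F be the rest, immediate and 5-minute values. Using change from rest instead of raw values gives (F − R) − (I − R) = F − I, so R drops out. For a true shift d:

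| True pattern | (a) I − R | (b) F − R | (c) F − I |
|---|---|---|---|
| No effect | 0 | 0 | 0 |
| Fully sustained | d | d | 0 |
| Half lost | d | d/2 | −d/2 |
| Full return to rest | d | 0 | −d |
| Late onset | 0 | d | d |

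The stated contrast is (c). It cannot separate the first two rows. Columns (a) and (b) together separate all five. This step rests on no assumed effect size, correlation or test.

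**Step 2: size, under assumptions.** The documents give no SD, effect size, correlation or allocation ratio. Assume a shift of 0.8 SD, within-subject correlation ρ of 0.5 or 0.8, and 15 subjects per arm, with 30 pooled shown for comparison. The paired standardised effect is shift/√(2(1 − ρ)). The divisor is 1 at ρ = 0.5 and 0.632 at ρ = 0.8. A shift of 0.8 SD gives 0.80 and 1.26; a shift of 0.4 SD gives 0.40 and 0.63. Power of a paired t-test at two-sided 0.0125 (noncentral t):

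| Contrast and true pattern | n = 15 | n = 30 |
|---|---|---|
| (c), no effect | 1.25% | 1.25% |
| (c), fully sustained | 1.25% | 1.25% |
| (b), no effect | 1.25% | 1.25% |
| (b), fully sustained | 60–97% | 95–100% |
| (c), half lost | 13–38% | 34–78% |

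The 1.25% entries are simply the test level. Simulation agrees to within sampling error.

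**Step 3: does the primary test fill the gap?** In simulation with 15 per arm, the between-arm test rejects in 1.28% of trials when neither arm shifts, and in 1.28% when both shift by 1 SD. A shift common to both arms is invisible to it.

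**Step 4: precision of the missing estimates.** With 15 subjects the 95% half-width is 2.145/√15 = 0.55 SD at ρ = 0.5, and 0.55 × 0.632 = 0.35 SD at ρ = 0.8.

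**The case against.** The main stated aim is time dependence, and immediate versus 5 minutes does test change over time. Persistence is named only in the Risk/Benefit section, as a remark about missing literature and not as a hypothesis. No passage says that a non-significant result will be read as persistence. All of this stands. A reader might infer that the secondary question is worthless, or that the authors intend to read no difference as sustained; the documents support neither.

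Rest is also not ignored. The Brief Summary, the Background and the primary question name comparison with rest. Baseline values are reported by region, and the monitoring section has pre- and post-therapy impedance changes recorded. A reader of the results could see roughly whether values moved. But the detailed primary plan has two groups, I.S. and EzPAP, and no resting level. The Brief Summary mentions a one-way multivariate analysis of variance without naming its factor. Even a primary analysis realigned to rest would largely supply (a) and would still lack 5-minute minus rest.

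Finally, this is a secondary question in a 30-subject proof-of-concept study. That limits the weight of the point, and it favours estimates over more testing.

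**Conclusion.** The point holds in limited form. The stated contrast answers whether the pattern changes between the end of therapy and 5 minutes later. It does not answer whether redistribution occurred or remains, and the statistical section specifies no test or estimate of change that would. The cancellation is exact. The rejection rates depend on the assumed 0.8 SD shift, the correlation of 0.5 to 0.8, the 15-per-arm split and a paired test, which the plan does not specify.

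A reader might go further and say that a significant result misleads when half the effect persists. It does not: change over time is then the correct answer, and only the further step to *nothing remains* is unsupported. The plan should be amended, but this does not threaten the primary comparison of devices.

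**What to change.** In the secondary research question and in Statistical Considerations, item 5:

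- Keep (c), 5-minute minus immediate, as the stated secondary contrast.
- Add within-subject estimates with confidence intervals, by region and arm, of (a) immediate minus own eupneic baseline and (b) 5-minute minus own eupneic baseline.
- Conclude that redistribution remains at 5 minutes only if (a) and (b) both differ from zero in the same direction. With no effect, both are significant in about 0.1% of simulated trials.
- State that a non-significant (c) does not show persistence. Likewise, a non-significant (b) does not show return to rest: with half the effect left, (b) has the same 13–38% power at n = 15 as (c).

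If formal tests are wanted, test (a) first and, if it is significant, test (b) and (c) each at 0.0125. Since (a) = (b) − (c), a true non-zero (a) means that (b) and (c) cannot both be null, so the error rate per region stays at 0.0125. State whether this is done per arm or pooled: four chains sum to 4 × 0.0125 = 0.05, and eight (four regions, two arms) to 8 × 0.0125 = 0.10. Ungated, 12 pooled tests sum to 0.15.

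A strict sequence of (a), then (b), then (c) should not be used. If the effect returns fully to rest, (b) is null and the sequence stops. Decay is then called in at most about 1.3% of simulated trials, against 60–100% for (c) alone.

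The cost is wording and two more contrasts per region on recordings already planned. The gate has its own price: a late-onset change would not be formally tested, and under full decay (a) and (c) are both significant in 43–94% of trials at n = 15, against 60–97% for (c) alone. Estimates without the gate avoid both losses.

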**Answer/Response:**

**PRIMARY NULL HYPOTHESIS:**

There is no difference in regional distribution of ventilation when comparing Incentive Spirometry (I.S.) lung expansion therapy to EzPAP® lung expansion therapy in healthy adult human subjects

**Alternative hypothesis:** There is a difference in regional distribution of ventilation when comparing Incentive Spirometry (I.S.) lung expansion therapy to EzPAP® lung expansion therapy in healthy adult human subjects?

- Independent variable
  - Lung expansion therapy
    1. Incentive Spirometry

2. EzPAP®

- Dependent variables
  - Regional distribution of ventilation areas of interest
    1. Ventral end-expiratory lung volume impedance
    2. Mid-ventral end-expiratory lung volume impedance
    3. Mid-dorsal end-expiratory lung volume impedance
    4. Dorsal end-expiratory lung volume impedance
- Statistical analysis
  - Frequency (n) and percentage (%) will be used to report descriptive categorical level data.
  - Shapiro-Wilk test of normality will be applied to evaluate distribution of continuous level data. Normally distributed data will be presented as mean and standard deviation and 95% confidence interval. Effect size will be reported as Cohen's *d*.
  - Non-normally distributed data will be reported as median and interquartile range. Effect size will be reported as *r*.
  - Independent samples t-test will be applied to normally distributed continuous data to compare group means, and Mann Whitney-U test will be applied to non-normally distributed data.
  - Statistical significance set a  $P$  (2-tailed)  $\leq .0125$  to reduce risk of Type I error.

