**EzPAP® POSITIVE AIRWAY PRESSURE GROUP**

- A study investigator will provide instruction on EzPAP® procedure performance before supervised therapy and monitoring begins. A second study investigator will perform EIT device set-up and monitoring only.
- Five minutes of eupneic ventilation EIT monitoring will occur before EzPAP® therapy commences.
- Study participants will be asked to breathe normally through the EzPAP® device’s mouthpiece for 10 breaths, followed by a 60 second pause.
- The 10-breath cycle will be repeated three times with respiratory therapist coaching.
- Five minutes of eupneic ventilation EIT monitoring will occur following the last EzPAP® lung expansion therapy breath cycle.
- EzPAP® therapy and monitoring sessions will last about 15 minutes (See image).

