**REGIONAL DISTRIBUTION OF VENTILATION MONITORING:**

- PulmoVista monitoring and lung expansion therapy will occur only one time as described above. .
- The following information will be displayed on the PulmoVista 500 device’s main monitoring screen during lung expansion therapy, but study investigator staff administering therapy and study participants will be blinded from information displayed on the screen’s monitor during therapy session in an effort to reduce performance bias:

[figure not shown]
A: Dynamic imaging showing impedance changes in a caudo-cranial image referenced to a dynamic baseline.  
 B: Tidal image showing EELI during inspiration and exhalation of the last detected breath.  
 C: Global impedance waveform showing relative impedance changes across electrode plane.  
 D: Regional impedance waveforms  
 F: Tidal respiratory rate  
 G: Global tidal variation displayed as 100%.  
 H: Regional tidal variation displayed as a percentage of global tidal variation.  
 - Once lung expansion therapy

IRB-HSR # 19661: A descriptive observational pilot study comparing regional distribution of ventilation during lung expansion therapy in healthy human subjects

session has ended, the researcher will detach trunk cables from electrode cables, detach reference electrode snap from adhesive ECG electrode, unclamp the electrode belt, and then remove belt from the study subject. Subject participation in this study is considered complete at this time.

- Inspect of electrode belt contact area will be performed to assess for evidence of skin irritation or bruising. Study participant will be notified by study investigator at the time of skin assessment if significant skin irritation or bruising is present. Finding will be recorded by study investigator.

- Displaying changes
  - The following information will be displayed and used to record pre and post lung expansion therapy end-expiratory lung impedance changes:

- Electrode belt, patient cable, and PulmoVista 500 EIT device (Draeger; Lubeck, Germany) will be removed study participant’s room and returned to a storage location outside of patient care areas.
- Following each EIT to subject interface disconnect, an alcohol, aldehyde, or quaternary ammonium based compound will be soaked on a wipe cloth to disinfect the surfaces of the patient cable, electrode belt, trunk cable, and EIT unit.

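### The secondary time question compares two readings in the same participants, but the plan gives it only tests for independent groups

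*Combined protocol and SAP*

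**What the plan says.** Under Hypothesis to be Tested, the single secondary question concerns "regional redistribution of ventilation measured immediately after lung expansion therapy when compared to regional distribution of ventilation measured 5-minutes after lung expansion therapy". The Abstract states the same aim: "We are also interested in determining if regional redistribution of ventilation is time dependent". The Background describes the contrast as one between readings taken "immediately after the third lung expansion therapy breathing sequence and post-lung expansion therapy session baseline measurement".

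The procedures put both readings in one recording of one person. In the I.S. arm, "Five minutes of eupneic ventilation EIT monitoring will occur following the last I.S. lung expansion therapy breath cycle". In the other arm, "Five minutes of eupneic ventilation EIT monitoring will occur following the last EzPAP® lung expansion therapy breath cycle". The monitoring section adds that "PulmoVista monitoring and lung expansion therapy will occur only one time as described above".

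For the analysis, Statistical Considerations question 5 (secondary variables) only refers back to question 4. There, the sole independent variable is the device, the four dependent variables are regional end-expiratory impedances, and "Independent samples t-test will be applied to normally distributed continuous data to compare group means", with Mann-Whitney U for non-normal data, at two-sided 0.0125. The Abstract says of the primary hypothesis that "the difference between continuous level data will be analyzed with one-way multivariate analysis of variance", which is also a between-groups method. No paired, signed-rank, repeated-measures or mixed-model analysis appears anywhere, and time is never listed as a factor.

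**The concern.** The question is about change within a person, and the tests assigned to it compare separate groups of people. If the two times are entered as the two groups, 30 people become 60 supposedly independent readings and the pairing is discarded. If the two devices are entered as the groups, the test asks something else.

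What is at stake is the study's answer on whether redistribution lasts. The Risk/Benefit Analysis (question 1) says the investigators found no previous research on whether it is sustained after I.S. or EzPAP. A real fade over the five minutes could be missed and reported as no difference, which would read as a sustained effect.

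**Working it through.** **Structure.** There are two ways to follow the cross-reference.

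- Groups are the two times. The independence assumption fails by design, because every participant is in both groups.
- Groups are I.S. and EzPAP, for example on each person's change. Independence holds, but the test asks whether the change differs by device. Whether there is a change at all has no test.

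Either way, the question as worded lacks a suitable analysis. This step uses no assumed number.

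**The plan's own figures.** The sample size is 30, stated to be without a power analysis, so there is no power figure to reproduce. The threshold fits 0.05/4 = 0.0125, one test per region. The base of 0.05 and the divisor are inferred; the documents do not give them.

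**Inputs for the size.** From the documents: n = 30 with no dropout expected, and two-sided 0.0125. Assumed: equal SDs σ at the two times, normal data, a mean shift of d SDs, and within-person correlation ρ. A range is shown because the documents give neither d nor ρ.

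**Standard errors.** The independent test uses σ√(2/n). The true value is σ√(2(1−ρ)/n). The ratio is 1/√(1−ρ): 1.20 at ρ = 0.3, 1.41 at 0.5, 1.83 at 0.7 and 2.24 at 0.8.

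**Paired test.** The noncentrality is d√n/√(2(1−ρ)). For d = 0.5 and √30 = 5.48:

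- ρ = 0.3: 2.74/1.18 = 2.31
- ρ = 0.5: 2.74/1.00 = 2.74
- ρ = 0.7: 2.74/0.775 = 3.54
- ρ = 0.8: 2.74/0.632 = 4.33

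**Power.** The figures come from 100,000 simulated trials per setting. The paired results were checked against the noncentral t.

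| d | ρ | Independent | Paired |
|---|---|---|---|
| 0.3 | 0.3 | 5% | 12% |
| 0.3 | 0.5 | 3% | 17% |
| 0.3 | 0.8 | 0.4% | 48% |
| 0.5 | 0.3 | 24% | 38% |
| 0.5 | 0.5 | 20% | 54% |
| 0.5 | 0.7 | 16% | 80% |
| 0.5 | 0.8 | 12% | 94% |
| 0.8 | 0.5 | 76% | 95% |
| 0.8 | 0.8 | 84% | >99% |

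At d = 0.5 the share of paired power lost is 1 − 0.2355/0.3789 = 38% at ρ = 0.3 and 1 − 0.2023/0.5382 = 62% at ρ = 0.5. At d = 0.8 and ρ = 0.5 it is 1 − 0.7588/0.9501 = 20%.

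The loss depends on the effect size because the independent statistic centres near d√(n/2) whatever ρ is. That is 0.5 × √15 = 1.94 for d = 0.5 and 0.8 × √15 = 3.10 for d = 0.8. The threshold is about 2.50 (normal quantile, upper tail 0.00625). Higher correlation tightens the statistic around its centre, which is below the threshold in the first case and above it in the second.

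**Actual level of the independent test** (d = 0, n = 30, nominal 0.0125): 0.0034 at ρ = 0.3, 0.0006 at 0.5 and 0.0001 at 0.7.

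**The case against.** The strongest reply has four parts.

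- This is one secondary question in a 30-person proof-of-concept study that calls itself descriptive and claims no power. That stands, and it limits the severity. It does not supply a test, and the plan does set a formal significance threshold.
- The plan also reports means, SDs, 95% confidence intervals and Cohen's *d* (or medians, IQRs and *r*), so a fade could be seen descriptively. That stands in part: the risk lies in the formal conclusion, not in the data being hidden.
- Since question 4 names device as the independent variable, the cross-reference may mean a device comparison of change. That is a fair reading, and on it the power loss does not arise. The time question is then simply untested.
- The alternative hypothesis that repeats the null is a copying slip; the primary question has the correct form. That stands. With a two-tailed test it changes no calculation.

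A reader might also infer that the broken independence produces false positives. Under positive correlation it does the opposite. Only a negative correlation would inflate the error (about 0.028 at −0.3, normal approximation), and nothing in the documents suggests one.

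**Conclusion.** The mismatch is established from the text alone: the contrast is within participants, and every test named is for independent groups. The plan as written either ignores the pairing or leaves the question unanswered.

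The size is conditional on assumed values. For a 0.5 SD change with all 30 participants, power with the independent rather than the paired test falls from 38% to 24% at correlation 0.3, from 54% to 20% at 0.5, from 80% to 16% at 0.7 and from 94% to 12% at 0.8.

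A reader might conclude that the plan loses most of its power. The documents do not support that as a general statement: the loss is modest for weak correlation or for a 0.8 SD change (95% to 76% at correlation 0.5), and it applies only if the tests are run on the two times. Nor could persistence be missed, since persistence is itself no difference; only a fade could. The primary device comparison is not affected. This should be fixed, but it is not a bar to the study.

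**What to change.** In Statistical Considerations question 5, replace the cross-reference with a within-participant analysis for each of the four regions, pooled over arms because the secondary question does not split by device. The variable is the difference, 5 minutes post minus immediately post. Test it with a paired t-test, or with Wilcoxon signed-rank when the normality rule of question 4, applied to the differences, calls for it, at 0.0125 per region.

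Pooling also keeps the number of tests at four. Testing by arm would give eight at 0.0125, a family-wise error of 1 − 0.9875^8 = 9.6% if independent, against 1 − 0.9875^4 = 4.9%.

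Report device differences in that change separately, labelled exploratory: an independent-samples test on the change scores, or an arm-by-time term in a mixed model. These answer a different question and do not replace the paired test.

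State which stretch of the recording supplies each reading, since the Background and the hypothesis section describe the later point differently. As a clerical correction, make the secondary alternative hypothesis say that there is a difference.

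The cost is a short protocol amendment. No new data are needed.
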